A pilot project to investigate
the use of an external
vestibular prosthesis potential
to improve clinical
management of Chronic
Subjective Dizziness (CSD)

NCT# 02048670

July 22, 2013

IRB Minimal Risk Protocol Template

General Study Information

Principal Investigator: [name].

Study Title: A pilot project to investigate the use of an external vestibular prosthesis potential to improve clinical management of Chronic Subjective Dizziness (CSD)

Protocol version number and date: 01, 22 JUL 2013

Purpose

Hypothesis: #1 The use of the BalanceBelt™ will provide differential information about body sway movements during specific clinical balance and gait tasks in patients with CSD that is not currently available through routine measures.

Hypothesis: #2 The use of the BalanceBelt™ will provide for a more rapid rate of reduction in patient symptoms compared to the historical data from the traditional habituation therapy method.

Aims, purpose, or objectives: #1 Motion detectors contained in the BalanceBelt™ will be used to record information about the subtle changes in posture and gait that are thought to occur in patients with CSD with the tractors turned off. The goal of this portion of the study will be to improve diagnostic strategies for CSD.

Aims, purpose, or objectives: #2 In this second portion of the study we will test the benefits of a 1-week intensive rehabilitation program using the BalanceBelt™ with tractors activated in 10 patients with CSD. The goal of this study will be to develop a treatment that is quicker and more effective than current therapies.

Background (*Include relevant experience, gaps in current knowledge, preliminary data, etc.*):

Chronic subjective dizziness (CSD) is the second most common condition identified in patients referred to Mayo Clinic for persistent dizziness. We manage nearly 500 patients with CSD each year. CSD is a syndrome of persistent non-vertiginous dizziness and unsteadiness that may be worsened by patients' own motion, exposure challenging visual stimuli such as busy shopping areas, or performance of precision visual tasks such as reading. CSD develops in about 25% of patients following medical events that acutely disrupt balance. Once established, CSD may last for many years, even if the problems that triggered it resolves. As a result, CSD causes considerable distress and functional impairment, even to the extent of work disability and disruption of family and social life (Staab, 2012).

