We propose two preliminary studies using the BalanceBelt™ in patients with CSD. In the first study, we will use the motion detectors contained in the BalanceBelt™ to record information about the subtle changes in posture and gait that are thought to occur in patients with CSD. This goal of this study will be to improve diagnostic strategies for CSD. We will compare postural movements recorded with BalanceBelt™ with tactors turned off during quiet stance, normal walking (Dynamic Gait Index), functional reach test, and the Sensory Organization Test in 10 patients with CSD and 10 age and gender matched normal individuals. In the second study, we will test the benefits of a 1-week intensive rehabilitation program using the BalanceBelt™ with tactors activated in 10 patients with CSD. The goal of this study will be to develop a treatment that is quicker and more effective than current therapies.

References:

Staab, J.P: Chronic subjective dizziness. *Continuum Lifelong Learning Neurol* 2012; 18(5):1118–1141.

Subject Information – charts, records, images, or specimens are considered 'subjects'

Target accrual: *Proposed number of subjects to be included in your study at your site. "Subjects" may include Mayo Clinic charts, records, or specimens, and/or charts, records, or specimens received at Mayo Clinic from external sources for collaborating analysis by the investigator under this IRB application:*

Subject population: 20 patients with diagnosis of Chronic Subjective Dizziness (CSD) and 10 normal volunteers.

- Inclusion Criteria:
1. Subjects will be 25-70 years of age inclusive and pregnant women may participate.
 2. Patients will have CSD as their primary diagnosis for the cause of their balance and dizziness complaints provided by the Behavioral Medicine Program for Dizziness, a division of the Department of Psychiatry & Psychology.
 3. Normal volunteers will have a negative history of otologic & neurologic disorders and no history of dizziness and balance problems.
 4. Normal volunteers will have normal findings on a screening office examination for peripheral and central vestibular system involvement (see methods for details of the examination) and screening for normal or symmetrical hearing loss of explainable origin.

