- Exclusion Criteria:
1. Patients with positive indications from testing of peripheral and/or central vestibular system involvement that is felt to be influencing the symptoms reported beyond the CSD alone.
 2. Patients with mobility restriction that would prevent participating in the tests or the intensive therapy trials.
 3. Subjects with hearing impairment that interferes with oral communication.

Will a Certificate of Confidentiality be obtained? *If yes, provide an explanation.*

NO

Study Design

Methods: *Describe, in detail, the research activities that will be conducted under this protocol:*

For Hypothesis and aim #1: Ten consecutive patients, ages 25-70 years, diagnosed with CSD after completion of their routine evaluation in the Dizziness and Balance disorders laboratory and their evaluation by the Behavioral Medicine program for dizziness, would then be recruited for participation in the study. If they agree to participate they will individually be placed through the following evaluations while wearing the BalanceBelt™ with the tractors turned off but the recording elements turned on. Each of these tests is a standard evaluation tool used in the Vestibular and Balance Laboratory on a routine basis:

1. Dynamic Gait Index – evaluates gait under normal walking and under conditions of head turns, walking around two objects on the floor, stepping over a shoe box, walking at different speeds, walking with a stop and 180 degree turn, walking up and down 3 standard steps with hand rails. During the evaluation the physical therapist or the audiologist guards the subjects at all times walking with the subject and the subject wears the harness used for the test in #3 that has a hand grab to prevent falls.
2. Functional Reach Test – the subject stands in a stationary position and reaches out with a single arm as far as they can without taking a step. Here again the physical therapist or the audiologist is guarding the patient during the performance of the test, again with the subject in the harness used in #3 with the hand grab to prevent falls.

3. Sensory Organization Test – this is a 6 condition standard evaluation of balance control performed on a dynamic platform that can record sway movement in the A/P dimension while the sensory inputs from proprioception and vision are varied through the platform and visual surround movements. The subject wears a full chest harness that is fastened to a roll bar above the subject to prevent any falls.

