For each of the patients an age and gender matched normal (± 5 years) volunteer will go through the same evaluations. The time for testing will take 45 minutes. Normal subjects will be recruited through written advertisements from visitors and / or accompanying persons for patients to Mayo Clinic. Each of the normal subjects will go through an office vestibular examination that will consist of direct monitoring for nystagmus in all positions of gaze with and without visual fixation present. They will also undergo the head thrust test with visual fixation present and headshake test with visual fixation absent. Pursuit and saccade office examination will be performed with a hearing screening by pure tones only. If any abnormalities are revealed with the screening the normal volunteer will be advised as to formal testing that should be performed via their primary care physician also being notified.

For Hypothesis and aim #2: Ten consecutive patients, ages 25-70 years, diagnosed with CSD who live within a 30 minute drive time of the Rochester Mayo campus will be asked to participate in the habituation therapy activities typically used as treatment of CSD but with an intensive treatment program using the exercises at home for the week. The patients will be using the BalanceBelt™ with the tractors activated. The typical therapy evaluations pre-therapy will be taken in addition to Visual Analog Scales related to the intensity of symptoms provoked by visual motion, head movements and walking in visually complex environments. These same measures will be taken at the end of the week of intensive therapy at a return visit to check their exercise activities prior to continuing their progressive home treatment. The one week of intensive therapy will be performed prior to starting any recommended medications or medication changes for the CSD. The therapy will be conducted by one of the Physical Therapists certified in Vestibular and Balance therapy.

Following the intensive therapy the patient will continue with the therapy activities and medication trials as is standard currently for the CSD patients.

Resources: *Describe the available resources to conduct the research (personnel, time, facilities, mentor commitment, etc.):*

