Subject Identifiers: Individually identifiable information, including demographic data, that identifies the individual or for which there is reasonable basis to believe it can be used to identify the individual. NOTE: Identifiers apply to subjects enrolled in your study and to the subject’s relatives, household members, employers, etc.

Internal refers to subject identifiers that will be included in the dataset maintained by the study team.

External refers to subject identifiers that will be shared with persons outside of the immediate study team, for example, sent to an external collaborator or shared with a national registry.

SUBJECT IDENTIFIERS Check all that apply	INTERNAL IDENTIFIER	EXTERNAL IDENTIFIER
Name		
Social Security number		
Medical record/patient registration number, lab accession, specimen or radiologic image number	x	
Study number, subject ID, or any other unique identifying number, characteristic or code that can be used to link the identity of the subject to the data	x	
Dates: All elements of dates [month, day, and year] directly related to an individual. Their birth date, date of death, date of diagnosis, etc. Note: Recording a year only is not a unique identifier.	x	
Medical device identifiers and serial numbers		
Biometric identifiers, including finger and voice prints, full face photographic images and any comparable images		
Web Universal Resource Locators (URLs), Internet Protocol (IP) address numbers, email address		
Street address, city, county, precinct, zip code, and their equivalent geocodes		
Phone or fax numbers		
Account, member, certificate or professional license numbers, health beneficiary numbers		
Vehicle identifiers and serial numbers, including license plate numbers		
If None of the above identifiers will be recorded or maintained in the dataset and/or sent outside of the study team, please check “None”.		

Statistical Information

Note: Power analyses and study endpoints are not needed for a pilot or feasibility studies.

No statistical information. *If checked, please explain:*

Statistical Considerations

Power Statement: Power analyses not used as this is a pilot study.

Data Analysis Plan:

For Hypothesis and aim #1: The outcome parameters from the BalanceBelt™ that represent the total amount of sway and sway activity in the A/P and M/L directions will be compare between the CSD patients and the normal age matched volunteers via the Wilcoxon rank-sum test for mean comparisons.

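### Hypothesis #1 claims sway information beyond routine measures, but the aim #1 analysis uses no routine result and does not set apart belt A/P and total sway during the SOT, where the platform can already record A/P sway

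*Combined protocol and SAP*

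**What the plan says.** All references are to the combined protocol and SAP.

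- **Purpose, Hypothesis #1.** The belt is to give differential information on body sway in CSD, and that information is to be of a kind "that is not currently available through routine measures".
- **Purpose, aim #1.** "The goal of this portion of the study will be to improve diagnostic strategies for CSD".
- **Background.** Belt movements in 10 patients and 10 matched normals are to be compared "during quiet stance, normal walking (Dynamic Gait Index), functional reach test, and the Sensory Organization Test".
- **Study Design, Methods for aim #1.** Three tests are listed: DGI, Functional Reach and SOT. "Each of these tests is a standard evaluation tool used in the Vestibular and Balance Laboratory on a routine basis". Item 3 describes the SOT as run on a "dynamic platform that can record sway movement in the A/P dimension". For each patient a matched normal "volunteer will go through the same evaluations".
- **Data Analysis Plan, aim #1.** The variables are given as "The outcome parameters from the BalanceBelt™ that represent the total amount of sway and sway activity in the A/P and M/L directions". They are compared between the groups by the Wilcoxon rank-sum test. No task is named and no routine result is used.
- **Endpoints.** None is fixed, because the study is a pilot.

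**The concern.** Hypothesis #1 has two parts. One is that belt sway differs in CSD. The other is that the belt shows something routine measurement does not. A comparison of belt values between groups addresses the first part. It addresses the second only where the belt signal is one that routine testing does not already provide.

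For A/P sway during the SOT, the protocol's own description says that a routine instrument can record it. If that signal differs between groups, the result fits two accounts: the belt has found something new, or it has picked up what the platform would also have shown. The planned analysis cannot tell these apart. A reader of the pilot report could then take such a difference as support for the whole hypothesis, including the clause that justifies using the belt for diagnosis.

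**Working it through.** The plan states no sample-size, power or effect figure for aim #1, so there is nothing to reproduce. The check sets the claim, the analysis and the description of the routine tests side by side.

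**Step 1: does any routine result enter the analysis?** The Data Analysis Plan lists three belt parameters (total, A/P, M/L) and one contrast (patients against normals). No DGI score, reach distance or SOT result appears as comparator, covariate, correlate or benchmark.

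**Step 2: where do the documents show overlap?** Cross the four tasks in the Background with the three belt parameters, counting one result per cell.

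| Task | A/P | M/L | Total |
|---|---|---|---|
| Quiet stance | none described | none described | none described |
| Walking (DGI) | none described | none described | none described |
| Functional Reach | none described | none described | none described |
| SOT | platform can record it | none described | partial, through A/P |

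This gives 4 × 3 = 12 cells. One overlaps directly and one in part, so 2 of 12, leaving 10. The Methods list omits quiet stance. On that list there are 3 × 3 = 9 cells, of which 2 overlap and 7 do not.

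Total sway is not defined in the plan. On the natural assumption that it combines the two directions, for example T² = A² + M², a group difference in A alone moves T even if M is unchanged. Excluding only the A/P cell would therefore leave the same signal in through total sway.

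**Step 3: does the plan separate the overlapping cells?** No. The Background says in which tasks movements will be compared. Neither it nor the Data Analysis Plan commits to reporting by task, and no section says whether SOT sway counts towards Hypothesis #1.

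**Step 4: could a correlation between belt and platform settle the matter?** Both groups undergo the SOT, so one could be computed. Average the within-group correlations over two groups of 10 on the Fisher z scale:

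SE = 1/√(7 + 7) = 1/√14 = 0.2673, so the 95% half-width is 1.96 × 0.2673 ≈ 0.5238.

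The documents give no value of r, so three are assumed:

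| Observed r | z | z limits | 95% CI for r |
|---|---|---|---|
| 0.5 | 0.5493 | 0.0255 to 1.0731 | 0.03 to 0.79 |
| 0.8 | 1.0986 | 0.5748 to 1.6224 | 0.52 to 0.92 |
| 0.9 | 1.4722 | 0.9484 to 1.9960 | 0.74 to 0.96 |

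The intervals are wide. Measurement noise also lowers r, so a low value would not show that the belt carries new information. The correlation can describe the overlap but cannot decide the question.

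**The case against.** The best defence has four parts.

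1. **There is no counting rule to be wrong.** The study is a pilot with no fixed endpoints, so the plan never says that an SOT A/P difference confirms Hypothesis #1. This stands. A reader might infer that the plan would count a repeat of the platform reading as success, but the documents do not say so. They are silent, and the silence is the gap. The template's pilot waiver covers power analyses and endpoints. It does not cover agreement between a hypothesis and its analysis.
2. **Most planned outputs are unaffected.** This also stands. M/L sway, and sway in gait, reach and quiet stance, are not described as routine outputs, so a group difference there fits the hypothesis as worded. A reader might infer that Hypothesis #1 as a whole has no matching analysis. That goes too far.
3. **Belt and platform need not measure the same thing.** Correct. The belt is worn at the waist, and the documents say only that the platform can record A/P sway. They do not show that the two readings are equivalent or closely related. Redundancy is a possibility that the analysis leaves open, not an established fact.
4. **Added diagnostic value is not the hypothesis.** Improving diagnosis is the goal of this portion of the study, while the hypothesis speaks of information. The plan therefore need not demonstrate better discrimination than routine scores. What remains is that a group difference in any belt signal should not be reported as if it had shown this.

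**Conclusion.** The point holds in a limited form. The clause about routine measures is not examined by any planned comparison with a routine result. For belt A/P sway during the SOT, and for total sway there to the extent that A/P drives it, a group difference cannot by itself support that clause. This follows from the text and needs no assumed effect size.

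It affects 2 of the 12 task-by-parameter results (2 of 9 on the Methods list), one of them only in part and only if total sway includes an A/P component. How often a misleading result would arise cannot be calculated: the documents give no effect size, standard deviation or belt-platform correlation. The point bears on what the pilot may conclude, not on its conduct. It is minor, or at most a modest should-fix.

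**What to change.** Amend the aim #1 Data Analysis Plan in one of two ways.

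**(A) Keep the claim and make it examinable.** Report belt parameters by task and by direction. Record the DGI, Functional Reach and SOT results from the tests both groups already undergo, and show their group comparisons beside the belt results. State that belt A/P or total sway during the SOT alone will not count as support for Hypothesis #1. A within-group correlation of belt and platform A/P sway during the SOT, with its 95% CI, may be added as description only. It should carry a note that it will be imprecise and that a low value does not prove new information.

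**(B) Narrow the claim.** Restate Hypothesis #1 as a between-group difference in belt-recorded sway, with no statement about routine measures.

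Option A costs some data recording and a few more descriptive tables, with no new procedures or subjects. Option B costs one reworded sentence and a more modest conclusion.

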Over the last decade, the Mayo Clinic Integrated Neurotology team, and other investigators around the world have developed two treatment strategies for CSD. One uses serotonergic medications such as sertraline (Zoloft) and venlafaxine (Effexor). The other is a variation of vestibular and balance exercises known as vestibular habituation. These therapies reduce symptoms for 60-80% of patients when administered by experts in the field

(Staab, 2012). However, they have important shortcomings. They are time-consuming, taking a minimum of 2-3 months of diligent treatment to achieve best results. They usually achieve a partial reduction in symptoms, which improves patients' functioning, but falls short of a cure. They can make patients worse, rather than better, when used by clinicians who are unfamiliar with them.

A new theory about altered postural control mechanisms in CSD suggests that it could be diagnosed more accurately and treated more quickly by using an external vestibular prosthesis to enhance sensory feedback during vestibular exercises. A suitable prosthesis is the BalanceBelt™, which is currently in final beta testing by BalanceTek, the company that developed it. This device has been shown to have efficacy in reducing sway behavior in patients that have bilateral vestibular hypofunction (Sienko et al, 2010). For those patients with deficient vestibular systems the belt provides information that is missing from the lack of vestibular system cues for detecting sway or leaning behavior, hence drawing attention to the information that is missing. The BalanceBelt™ is a comfortable, self-contained unit worn under the clothes around the waist. It has sensitive motion detectors and small tactors that vibrate against the skin at four locations to provide information about posture and motion. Patients with CSD do not have permanent vestibular deficits, but underutilize vestibular signals because they develop visual or somatosensory dependence. We expect the BalanceBelt™ to reset this error by providing patients with reliable motion stimuli.

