All of the equipment and procedures described above are already in place and used routinely by the Audiologists and Physical therapists that work in the Dizziness and Balance Disorders Center on Gonda-12 in the department of Otolaryngology. The only acquisition is that of the BalanceBelt™ for which the department of Otolaryngology research committee has approved a request for \$7800 from the small grants program to cover the cost of the belt (\$6000) and the 30% indirect costs (\$1800).

Check all that apply. If none apply, leave blank:

The research involves contact or interaction with subjects, for example, surveys, questionnaires, observation, blood draw.

Blood Collection

If this study involves prospective blood collection by finger, heel, ear stick or venipuncture, complete the following:

From healthy, non pregnant, adult subjects who weigh at least 110 pounds. For a minimal risk application, the amount of blood drawn from these subjects may not exceed 550ml in an 8 week period and collection may not occur more frequently than 2 times per week.

Volume per blood draw: _____ ml

Frequency of blood draw (e.g. single draw, time(s) per week, per year, etc.) _____

From other adults and children considering age, weight, and health of subject. For a minimal risk application, the amount of blood drawn from these subjects may not exceed the lesser of 50 ml or 3 ml per kg in an 8 week period, and collection may not occur more frequently than 2 times per week.

Volume per blood draw: _____ ml

Frequency of blood draw (e.g. single draw, time(s) per week, per year, etc.) _____

Review of Chart, Images, Specimens

Provide the date range for collection of data and/or specimens that will be included in your research dataset.
(*Example: 01/01/2000 to 12/31/2012*)

Date range: From _02/01_/2014 to 01/_31/2015

Check all that apply:

This study involves only data and/or specimens that will be collected after submission to the IRB.

Data Confidentiality, HIPAA Subject Identifiers

Review the list of subject identifiers below and, if applicable, check the box next to each subject identifier being recorded at the time you are collecting/abstracting data/specimens for use in this study.

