For Hypothesis and aim #2: The visual analog scale scores pre & post the week of intensive therapy will be compared for the 10 subjects using also the Wilcoxon test for mean comparisons.

Endpoints

As this is a pilot study no fixed endpoints will be used.

Primary:

Secondary:

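### Hypothesis #2 claims faster improvement than historical habituation therapy, but the Aim #2 analysis only compares patients with their own baseline

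*Combined protocol and SAP*

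**What the plan says.** - **Purpose, Hypothesis #2:** the belt "will provide for a more rapid rate of reduction in patient symptoms compared to the historical data from the traditional habituation therapy method". The Aim #2 goal is comparative too: a treatment that outdoes existing ones in speed and effect.
- **Study Design, Methods, aim #2:** one group of ten patients is measured before therapy and again at the end of one week, on visual analog scales (VAS) and the usual therapy evaluations. They do habituation exercises wearing the activated belt, "with an intensive treatment program using the exercises at home for the week".
- **Data Analysis Plan, aim #2:** "The visual analog scale scores pre & post the week of intensive therapy will be compared for the 10 subjects". This is the only analysis for Hypothesis #2. The method is given only as "using also the Wilcoxon test for mean comparisons". The aim #1 paragraph just before it names the rank-sum test, so it is unclear whether the aim #2 test is paired.
- **Background:** existing therapies reduce symptoms in 60-80% of patients, "taking a minimum of 2-3 months of diligent treatment to achieve best results".
- **Subject Information:** "20 patients with diagnosis of Chronic Subjective Dizziness (CSD) and 10 normal volunteers". **Review of Chart, Images, Specimens:** "Date range: From _02/01_/2014 to 01/_31/2015". Neither entry mentions a historical habituation group.
- **Power Statement and Endpoints:** as a pilot, the study has no power analysis and no fixed endpoints.

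**The concern.** The hypothesis and its analysis ask different questions. The hypothesis contrasts two rates of improvement: belt programme against past habituation therapy. The analysis contrasts two time points in one group. Its null hypothesis is no change over the week, and the historical rate does not enter it.

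Patients given ordinary habituation exercises may also improve in a week. A significant pre-post result is therefore what one could see if the belt programme were no better than usual care. A non-significant result would not refute the hypothesis either. The risk is that a positive within-group test is reported as evidence of faster recovery and used to justify further development on that basis.

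**Working it through.** The plan gives no effect size, alpha, sidedness or power for aim #2, so there is no figure to reproduce. The first two steps are textual; the rest illustrate size under stated assumptions.

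**1. Hypothesis against test.** Let μ be the mean one-week VAS improvement with the belt programme and μ_H the mean one-week improvement with ordinary habituation therapy. Hypothesis #2 is μ > μ_H. The planned test addresses μ = 0. The two coincide only if μ_H = 0, which the protocol does not assert.

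**2. Can the Background figures serve as μ_H?** No. They pool medication with habituation, are not VAS values, give no one-week change and are not cited in the analysis plan. If the 60-80% were nonetheless used as a response benchmark with n=10, the exact one-sided error rates would be:
- p0 = 0.60, at least 9 of 10 responding: 10 × 0.6⁹ × 0.4 + 0.6¹⁰ = 0.046
- p0 = 0.70, all 10 responding: 0.7¹⁰ = 0.028
- p0 = 0.80, all 10 responding: 0.8¹⁰ = 0.107, so no rule reaches 0.05

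**3. How often the planned test is significant with no advantage over habituation.** Assumptions: n=10, two-sided 0.05, normal scores, and μ = μ_H = d, where d is in SDs of the change scores. The range of d is assumed.
- *Paired reading, exact signed-rank.* The critical value is W ≤ 8 and the actual size is 2 × 25/1024 = 0.0488 (400,000 simulations).
- *Unpaired reading, exact rank-sum, 10 v 10.* The critical value is U = 23 and the nominal size 0.043 (200,000 simulations). The SD of a change is √(2(1−ρ)) times the SD of a score, where ρ is the pre-post correlation. That factor is 1.00 at ρ=0.5 and 0.775 at ρ=0.7.

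| d | Signed-rank | Rank-sum, ρ=0.5 | Rank-sum, ρ=0.7 |
|---|---|---|---|
| 0.1 | 5.8% | not run | not run |
| 0.2 | 8.5% | 1.9% | 0.5% |
| 0.3 | 13.1% | not run | not run |
| 0.5 | 28.1% | 10.3% | 3.6% |
| 0.8 | 59.6% | 32.2% | 14.5% |
| 1.0 | 78.4% | 52.6% | 28.3% |

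The signed-rank rates count both directions. At d = 0.1, about 1.2 percentage points are significant worsening.

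**4. With a benchmark.** Subtracting a fixed, known μ_H from each change restores the signed-rank size to 4.9%. Power for an advantage of 0.5, 0.8 or 1.0 SD is then 28%, 60% or 78%. If the benchmark were itself estimated from m patients with the same SD, the variance of the difference (in SD² units) would rise from 1/10 to 1/10 + 1/m, so these figures are the best case.

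**5. Precision of a within-group estimate.** The 95% t-interval half-width is t(0.975, 9)/√10 = 2.262/3.162 = 0.715 SD of the change scores.

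**The case against.** The strongest reply is that this is a pilot. It expressly forgoes power and fixed endpoints, the Aim #2 goal is a development aspiration, and the aim itself (testing the benefits of the week) is something a pre-post comparison addresses. This narrows the point: the main mismatch is in the wording of Hypothesis #2, and the study can still run. But pilot status excuses imprecision and missing power. It does not supply a comparison that the sponsor chose to state.

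Second, a usable historical value may exist. The usual therapy evaluations are repeated at one week, and the clinic manages nearly 500 such patients a year. That is an inference: the protocol neither says such values exist nor gives those evaluations any analysis. It is a reason to leave the benchmark route open.

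Third, the simulated rates span 0.5% to 78% and rest on assumed inputs. That is correct. They show that the size of the problem cannot be known from the plan, and the logical point does not need them.

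Fourth, the accrual and date-range entries are weak evidence, since a published or aggregate benchmark could lie outside both. They are consistent with no comparison being planned, and no more than that.

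**Conclusion.** The concern holds. The one analysis assigned to Hypothesis #2 cannot answer it, and nothing elsewhere in the document fills the gap. This conclusion rests on the text alone.

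Its practical size is conditional. With a paired test at two-sided 0.05 and normal scores, the chance of a significant result without any advantage over habituation is 6-13% if ordinary therapy yields 0.1-0.3 SD in a week, and 28-78% if it yields 0.5-1.0 SD. An unpaired reading gives lower rates.

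Even a sound benchmark would leave a limit. The programme differs from ordinary therapy in intensity as well as in the belt, so a gain could not be credited to the belt. The point should be fixed, but it does not prevent the study from running.

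**What to change.** **Main route, wording only.**
- Restate Hypothesis #2 and the Aim #2 goal as estimating the within-patient one-week change in VAS scores under the intensive BalanceBelt programme, with a 95% confidence interval.
- Name the paired (signed-rank) test.
- Remove the claim of greater speed and the reference to historical data.
- State that no conclusion will be drawn about current therapy, or about belt as distinct from intensity.

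**Alternative, only if a one-week habituation-only value on the same measure already exists.** Keep the comparative hypothesis and specify, before data collection, the benchmark, its source and its precision. Specify also the test against it: the difference and its confidence interval over the same week. If the value is for one of the usual therapy evaluations and not the VAS, add an analysis of that evaluation.

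**Cost.** The main route needs no new patients or data. The price is a more modest claim and a wide estimate, about ±0.72 SD of the change scores (a t interval for the mean, given as a guide). The alternative depends on a value that the protocol does not show to exist and, with ten patients, has low power for a moderate advantage.
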